12. Mandatory provision of blood for biomarker testing during the study
13. Signed declaration of consent after oral and written information about the protocol

* A woman is considered of childbearing potential (WOCBP), i.e. fertile, following menarche and until becoming post-menopausal unless permanently sterile. Permanent sterilisation methods include hysterectomy, bilateral salpingectomy and bilateral oophorectomy. A postmenopausal state is defined as no menses for 12 months without an alternative medical cause⁶⁰

Exclusion criteria

1. The patient has not recovered from surgery or is less than 4 weeks from major surgery
2. The patient has a history of life-threatening or severe immune related adverse events on treatment with another immunotherapy and is considered to be at risk of not recovering
3. The patient is expected to require any other form of systemic antineoplastic therapy or radiation therapy while receiving the treatment. However, radiation therapy treatment of non target lesion is allowed.
4. The patient has a history of severe clinical autoimmune disease
5. The patient has a history of pneumonitis, organ transplant, human immunodeficiency virus positive, active hepatitis B or hepatitis C
6. The patient requires systemic steroids for management of immune-related adverse events experienced on another immunotherapy
7. The patient has any condition that will interfere with patient compliance or safety (including but not limited to psychiatric or substance abuse disorders)
8. The patient is pregnant or breastfeeding
9. The patient is unable to voluntarily agree to participate by signed informed consent or assent
10. The patient has an active infection requiring systemic therapy
11. The patient has received a live virus vaccine within 30 days of planned start of therapy
12. Significant medical disorder according to investigator; e.g. severe asthma or chronic obstructive lung disease, dysregulated heart disease or dysregulated diabetes mellitus
13. Concurrent treatment with other experimental drugs
14. Concurrent treatment with Valproate or Xanthin Oxidase inhibitors
15. Known side effects to Montanide ISA-51
16. Any active autoimmune diseases e.g. autoimmune neutropenia, thrombocytopenia or hemolytic anemia, systemic lupus erythematosus, scleroderma, myasthenia gravis, autoimmune glomerulonephritis, autoimmune adrenal deficiency, autoimmune thyroiditis etc.
17. Severe allergy or anaphylactic reactions earlier in life

Evaluation before the start of treatment

The following parameters have to be performed within a month of the start of vaccinations (blood tests within two weeks):

- Medical history and clinical examination
- Performance status according to the ECOG scale
- Toxicity evaluation
- Concurrent medical intake
- Electrocardiogram

- Blood tests:
 - Hemoglobin, leukocyte differentiation count and platelets
 - Potassium, Sodium, Creatinine, albumin, uric acid, lactate dehydrogenase, Alkaline Phosphatase, Alanine transaminase (ALAT), amylase, bilirubin, ionized calcium, C Reactive Protein (CRP)
 - Hepatitis B, hepatitis C (IgG), HIV, HTLV-1(IgG), Epstein-Barr Virus EBV and Treponema.
- Pregnancy test: Women of childbearing potential must have a pregnancy test performed at the time of screening. This involves women who are not surgically sterilized or postmenopausal
- Diagnostic imaging: PET-CT, CT, or MRI scan of neck, thorax, abdomen, pelvis and optionally CNS and extremities depending on the cancer diagnosis.

Conduct of the study

Initial patient enrollment and treatment

A minimum of 2 treatments with the peptide vaccine have to be administered before inclusion of another patient for each of the first 3 patients included in the study.

1 st patient	1 st dose	2 nd dose	3 rd dose	4 th dose	5 th dose	6 th dose	7 th dose	9 th dose	10 th dose	
Safety evaluation			Go/no go for next patient							
2 nd patient				1 st dose	2 nd dose	3 rd dose	4 th dose	5 th dose	6 th dose	
Safety evaluation						Go/no go for next patient				
3 rd patient							1 st dose	2 nd dose	3 rd dose	
Safety evaluation before remaining patients' inclusion for remaining patients									Go/no go for remaining patients	
Dosing of remaining patients can start in parallel										x

Treatment plan and treatment schedule

Patients included in the protocol are treated with the ARG1-vaccine every third week for 48 weeks, whereupon no additional vaccinations will be given. In total, 16 vaccines will be administered. Each vaccine consists of 100 µg ARG1-18, 100 µg ARG1-19, and 100 µg ARG1-20 in 500 µl sterile water and 500 µl Montanide. In case of disease progression, patients are referred back to the oncology team, from which they were referred initially. Further treatment after disease progression will not be affected by participation in the study. Patients who receive all vaccines without progressive disease will have follow up appointments after 3 and 6 months in the experimental unit (EFEK) Herlev Hospital.

Detailed treatment and evaluation schedule

Series no.	Treatment every third week Evaluation after every fourth vaccine					
	Screening	1.	2.	3.	4.	
Day:		1	1	1	1	21 days
Year: 20__						
Treatment						
ARG1-peptide vaccine		0	0	0	0	
Signed consent form	0					
Anamnesis	0					
Physical examination	0	0	0	0	0	
Hight and weight	0					
CTCAE 4.0	0	0	0	0	0	
ECOG Performance status	0	0	0	0	0	
BP, Puls, Tp.	0	0	0	0	0	
Medication intake	0	0	0	0	0	
Blood test						
Ipilimumab male/female*	0	0	0	0	0	
12 HER EKS		0				0
p-HCG (if relevant)	0					
MM1413/MM1414 screening*	0					
Tumor evaluation						
CT scan of the cerebrum	0					
CT/PET-CT/MRI scan	0					0
Other						
EKG	0					
Tumor biopsy	0					0
DTH						0

Series no.	5.	6.	7.	8.	
Day:	1	1	1	1	21 days
Year: 20____					
Treatment					
ARG1-peptide vaccine	0	0	0	0	
Signed consent form					
Anamnesis					
Physical examination	0	0	0	0	
Hight and weight	0				
CTCAE 4.0	0	0	0	0	
ECOG Performance status	0	0	0	0	
BP, Puls, Tp.	0	0	0	0	
Mediaktion intake	0	0	0	0	
Blood test					
Ipilimumab male/female*	0	0	0	0	
12 HER EKS					0
p-HCG (if relevant)					
MM1413/MM1414 screening*					
Tumor evaluation					
CT scan of the cerebrum					
CT/PET-CT/MRI scan					0
Other					
EKG					
Tumor biopsy					
DTH					

Series no.	9.	10.	11.	12.	
Day:	1	1	1	1	21 days
Year: 20____					
Treatment					
ARG1-peptide vaccine	0	0	0	0	
Signed consent form					
Anamnesis					
Physical examination	0	0	0	0	
Hight and weight	0				
CTCAE 4.0	0	0	0	0	
ECOG Performance status	0	0	0	0	
BP, Puls, Tp.	0	0	0	0	
Mediaktion intake	0	0	0	0	

Blood test					
Ipilimumab male/female*	0	0	0	0	
12 HER EKS					0
p-HCG (if relevant)					
MM1413/MM1414 screening*					
Tumor evaluation					
CT scan of the cerebrum					
CT/PET-CT/MRI scan					0
Other					
EKG					

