The patient will be excluded subject to the following toxicities:

Blood sample	Criteria
Leukocytes	$< 1,0 \times 10^9$ ($\geq \text{grade 4}$)

Neutrophilic granulocytes	< 0,5 x 10 ⁹ (\geq grade 4)
Thrombocytes	< 25 x 10 ⁹ (\geq grade 4)
Hemoglobin	< 4 mmol/l (\geq grade 4)
Creatinine	>4,5 x ULM (\geq grade 4)
ASAT*	>8 x ULN (\geq grade 4)*
ALAT*	>8 x ULN (\geq grade 4)*

Other Adverse Events	
Bronchospasms or hypersensitivity reactions	\geq grad 3
Skin related AE	\geq grad 4
All other AE	\geq grad 3
Any eye pain or reduced visual of grade 2 or above with no restitution within two weeks will lead to exclusion	

*ASAT/ALAT grade 3 with bilirubin > 1,5 x ULN

** Bilirubin > 3 x ULN with ASAT/ALAT > 2,5 x ULN

Disease progression: Treatment is terminated if disease progression occurs according to RECIST 1.1 at predefined evaluation time points.

Patient request: The treatment can be stopped at any time if the patient wishes so.

Clinical judgement: The treatment can be stopped because of medical conditions at any time if the investigator finds it in the patients' best interest.

Other treatment: Patients will be excluded at any time if a new treatment with an experimental drug or other systemic anticancer treatment is initiated after inclusion in this protocol. The patient will be excluded if systemic treatment with corticosteroids is initiated unless it is on vital indication and in agreement with the physician responsible for the protocol. Supportive treatment is given on usual medical indication and is to be specified in the patient chart and flow sheets.

Pregnancy: A pregnancy test is to be performed before women of childbearing potential can be included in the study. Women of childbearing potential are to contact investigator immediately if pregnancy is suspected (absent or delayed menstruation etc.) at any point during the course of treatment and for 3 months after the end of treatment. A pregnancy test is performed if pregnancy is suspected and the participants can receive no more vaccination treatments and is terminated from the study if it turns out positive. A pregnant participant and the course of the pregnancy will be followed closely in the outpatient clinic.

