Delayed treatment: The patient is terminated from the study if the treatment is delayed more than 6 weeks. It is the responsibility of the principle investigator to assess the cause of delay and define the time point for the start of the delay. A patient can be delayed several times during the course of treatment without being excluded.

Early termination from the study

Participants, which are excluded from the study, will be referred back to the oncology team from which they came, for standard treatment. Patients that are excluded before the second vaccine will be replaced with new participants.

Concurrent treatment

- Supportive treatment is given based on clinical judgement and should be noted in the patient chart in accordance with existing practice
- Local palliative radiotherapy is allowed

Manufacture of the peptide vaccine

Peptide

For detailed description of peptide mixture production (see SOP “Fremstilling af ARG1-18,19,20 peptid til protokol AA1809” appendix 12.

The peptide sequence:

IO112	→	ARG 171-190; AKDIVYIGLRDVDPGEHYIL	→ARG1-18
		ARG 181-200; DVDPGEHYILKTLGIKYFSM	→ARG1-19
		ARG 191-210; KTLGIKYFSMTEVDRLGIGK	→ARG1-20

Peptides will be provided with above 90 % purity from external producer. Before administration they will be dissolved in sterile water, mixed and sterile filtrated through a 0,22 µm (30 mm Ø) filter.

Producing the peptide vaccine

The final production of the peptide vaccine will take place under GMP approved laboratory conditions (approved by the Danish Medicines Agency) which quality assures a sterile therapeutic product. It will take place in JM702, Herlev and Gentofte Hospital, authority number: 24223.

Montanide ISA 51

Montanide ISA 51 is produced and sold by Seppic INC: www.seppic.com. France. Montanide is delivered sterile and ready for use in ampules of 3 ml. Montanide ISA 51/Vaccine adjuvant is based on vegetable oil. See product resume or link: <http://www.seppic.com/human-health/vaccine-adjuvant/montanide-isa-51-@/1018/view-1042-seproduit.html>

Preparing the vaccine

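### A patient already taking a non-vital systemic corticosteroid can enter and stay, although starting the same drug after inclusion would exclude them

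*Combined protocol and SAP*

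**What the plan says.** **At entry.** Of the 17 exclusion criteria, only no. 6 names steroids, and it covers one indication: "The patient requires systemic steroids for management of immune-related adverse events experienced on another immunotherapy". The two criteria that bar concurrent drugs do not mention corticosteroids. No. 13 covers experimental drugs, and no. 14 reads "Concurrent treatment with Valproate or Xanthin Oxidase inhibitors".

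**During treatment.** Under Criteria for end of treatment, Other treatment: "The patient will be excluded if systemic treatment with corticosteroids is initiated unless it is on vital indication and in agreement with the physician". The doctor meant is the one in charge of the protocol.

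**Supportive care.** The Concurrent treatment section that follows Early termination from the study says: "Supportive treatment is given based on clinical judgement and should be noted in the patient chart in accordance with existing practice". Neither it nor the shorter paragraph on concurrent treatment after the follow-up table sets a steroid limit.

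**Indirect controls.** Exclusions 4, 5 and 16 remove patients by diagnosis: severe autoimmune disease in the history, pneumonitis or organ transplant, and active autoimmune disease. The list in no. 16 includes "autoimmune adrenal deficiency, autoimmune thyroiditis etc". Exclusion 7 covers the case where "The patient has any condition that will interfere with patient compliance or safety", and exclusion 12 covers a "Significant medical disorder according to investigator; e.g. severe asthma or chronic obstructive lung disease". Under Clinical judgement, "The treatment can be stopped because of medical conditions at any time" if the investigator thinks this is best for the patient.

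**Recording.** Concurrent medication is part of the evaluation before the start of treatment. The treatment schedule also lists medication intake at screening and at each vaccination visit.

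**The concern.** The on-treatment rule shows that the sponsor regards non-vital systemic corticosteroids as incompatible with staying in the trial. The entry criteria do not carry that judgement back to baseline, and nothing in the protocol explains the difference.

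The product is meant to boost ARG1-specific T cells. The secondary endpoint is the ARG1-specific T-cell response. Skin-infiltrating lymphocytes from the delayed type hypersensitivity (DTH) test are read as evidence that a functional response was induced. Autoimmunity is a named theoretical risk, and adverse events are the primary endpoint. If a corticosteroid taken throughout dampens T-cell induction or suppresses immune-related toxicity, both the immune and the safety readouts are affected in that patient. With 10 patients planned, each one carries weight.

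**Working it through.** No figure in the plan depends on this point, so the check sets the rules side by side.

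**Step 1. Test one case against every rule.** Take a patient with ECOG performance status 0 or 1 who is on a systemic corticosteroid for symptom control, with no vital indication and no autoimmune disease, pneumonitis or transplant. The indication is an assumed example; the protocol gives none.

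| Rule | Triggered? | Reason |
|---|---|---|
| Exclusion 6 | No | The steroid is not for an immune-related event on another immunotherapy |
| Exclusions 13, 14 | No | Corticosteroids are not among the drugs named |
| Exclusions 4, 5, 16 | No | They act on diagnoses this patient lacks |
| Exclusions 7, 12 | Only if judged so | They concern a condition or disorder; steroids are not named |
| Other treatment (on study) | No | Nothing is newly started |
| Clinical judgement (on study) | Only if the investigator chooses | Permits a stop, does not require one |
| Concurrent treatment sections | No | No steroid limit |
| Medication recorded at screening | No | Recorded, with no rule attached |

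The section on information and consent says that a patient who meets the criteria is included and treated straight away. As written, this patient enters.

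**Step 2. Check what *initiated* means.** The sentence just before the corticosteroid rule uses the same verb for other drugs and ties it to the time after inclusion. The natural reading is a new start, so continuing a baseline steroid does not trigger the rule.

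**Step 3. Compare two patients.** Same drug, same non-vital reason:
- Started after inclusion: excluded.
- Already in use at the first vaccine: no mandatory rule applies, at entry or later.

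**Step 4. Late correction.** Only patients excluded before the second vaccine are replaced. A discretionary stop after that loses 1 of 10 patients.

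**Step 5. Size.** An estimate would need the proportion of candidates on such steroids and the effect of steroids on ELISPOT, DTH or adverse events. The documents give neither.

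**The case against.** The strongest counter-argument is that the asymmetry may be deliberate. Immune responses are compared before, during and after vaccination within a patient. A steroid started midway disturbs that comparison, whereas a stable baseline steroid is present throughout. This is a reasonable thought, but the protocol does not state it and it does not close the gap. The DTH test is scheduled only after the 4th vaccine, so it has no pre-vaccine value to compare with. A steroid taken throughout could also still reduce the induction of a response or hide toxicity.

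A second objection is that no harm is documented. This stands in part. The protocol does not say that steroids blunt these assays or mask adverse events, and it gives no reason for its own on-treatment rule. The direction of effect is an assumption and its size is unknown. The inconsistency between the two rules does not depend on that assumption.

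A third objection is that control exists. This also stands in part. Exclusions 4, 5 and 16 are mandatory, and so is exclusion 7 once a condition is judged to interfere with safety. Medication intake is recorded at every vaccination visit, so a steroid user could be identified at analysis. A reader might infer that steroids at entry are uncontrolled; the documents do not support that. What is missing is a rule on the steroid itself.

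Finally, the immune analysis is secondary and descriptive, and ECOG 0 or 1 with a life expectancy of at least 3 months keeps the affected group narrow. Both limit the consequence.

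**Conclusion.** The gap holds on the text: a patient on non-vital systemic corticosteroids at entry, with no other excluding diagnosis, can be enrolled and kept, although the same drug started on study would exclude them. It is worth correcting because the change is cheap, not because damage to the results has been shown.

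The size is unknown. Blunted T-cell and DTH responses and masked immune toxicity are plausible, and rest on the assumption that corticosteroids act in that direction on these readouts.

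Two stronger readings are tempting, and neither is supported:

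- **A fixed bound on the response rate.** One patient in 10 is 1/10 = 10 percentage points, but this is not a ceiling. Patients stop at progression and may refuse the DTH test, so fewer may be evaluable; with 5 tested (assumed), one patient is 1/5 = 20 points. More than one patient could also be on steroids.
- **A reversed safety conclusion.** The plan calls treatment safe if fewer than 20% have grade 3-4 events, so 2/10 = 20% fails and 1/10 = 10% passes. Hiding one of two such events would change the reading, but nothing in the documents shows how likely that is.

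**What to change.** 1. **Add an exclusion criterion that mirrors the on-treatment rule.** Ongoing systemic corticosteroid treatment at the first vaccine excludes, with the same exception for a vital need agreed by the responsible physician. State that inhaled and topical use is not systemic. Physiological replacement can be handled under the vital-need exception. Check the criterion against the medication intake already recorded at screening and again at series 1, since the screening evaluation may be up to a month old by then.
2. **In Other treatment, change *is initiated* to *is initiated or continued*,** keeping the exception. Do not add a dose threshold: the present rule bars any non-vital systemic start, and a threshold would relax it.
3. **Identify any patient permitted on steroids** when immune responses and adverse events are reported, using the recorded medication intake.

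Exclusions 6 and 16 stay as they are.

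The cost is an amendment to two passages and one identification step in reporting, with no new visit. Because no dose limit is set, no dose data are needed beyond what is recorded. The downside is the loss of a small, unknown number of candidates on palliative steroids.

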During administration of the first 3 vaccines, the patient is observed for 30 minutes with measurements of pulse and blood pressure before and after the vaccine is given. The remainder of vaccines can be administered with observation of the patient for 15 minutes. Patients are observed for acute toxicities in the form of allergic reactions, including anaphylactic shock. Allergic reactions and/or anaphylactic shock will be treated per hospital guidelines.

The vaccines are ordered after contact to the project nurse at the clinical experimental unit (KFE) and to the manufacturing unit. (SOP: "Bestilling og håndtering af ARG1-18,19,20 peptid vaccine til patienter i protokol AA1809", appendix 14). When the vaccine is received, the "receipt of transport" is signed. (SOP: "Transport og udlevering af ARG1-18,19,20 peptid og Montanide, AA1809" appendix 15).

If the patient is prevented in attending the planned treatment day, the treatment can be moved to the following Tuesday or Thursday. If the treatment is postponed more than 6 weeks, patients will be excluded.

Criteria for treatment modifications

Delay of treatment

The treatment will be postponed if the patient experiences non-hematological AE grade ≥ 2 , except fatigue and skin related AEs such as local reaction at the injection site. Otherwise the following criteria are applicable:

Blood samples	Criteria
Leukocytes	$< 1,5 \times 10^9$ (grade 3)
Neutrophilic granulocytes	$< 1,0 \times 10^9$ (grade 3)
Thrombocytes	$< 50 \times 10^9$ (grade 3)
Hemoglobin	$< 5 \text{ mmol/l}$ (grade 3)
Creatinine	$> 3 \times \text{ULM}$ (grade 3)
ASAT	$> 5 \times \text{ULN}$ (grade 3)
ALAT	$> 5 \times \text{ULN}$ (grade 3)
Bilirubin	$> 3 \times \text{ULN}$ (grade 3)
Other AEs	
Skin-related AE	$\geq \text{grade 3}$
Fatigue AE	$\geq \text{grade 3}$
All other AE	$\geq \text{grade 2}$

The treatment will be postponed until CTCAE grade < 2 .

Criteria for end of treatment

1. Unacceptable toxicity (see adverse events)
2. Disease progression
3. On patient request
4. Clinical judgement
5. Other anti cancer treatment. However, radiotherapy treatment of to non target lesions is allowed.
6. Pregnancy
7. Delayed treatment

Unacceptable toxicity:

If treatment related AE grade 3-4 is not reduced appropriately within 12 weeks, the treatment will be stopped and the patient is excluded. Shorter delays can occur multiple times with no consequences for the patient or the trial.

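### Tumour scans follow the vaccine count rather than the calendar, so vaccine delays move the recorded date of progression and, on average, lengthen exploratory PFS

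*Combined protocol and SAP*

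**What the plan says.** All places are in the combined protocol and SAP.

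- **Scan timing.** The table under Detailed treatment and evaluation schedule is indexed by vaccine number and headed "Evaluation after every fourth vaccine". CT, PET-CT or MRI is marked at screening and then only in the 21-day column after vaccines 4, 8, 12 and 16. No calendar week or scan window is given. The 3- and 6-month follow-up scans count from the end of treatment.
- **Planned pace.** Patients are "treated with the ARG1-vaccine every third week for 48 weeks", and "In total, 16 vaccines will be administered" (Treatment plan and treatment schedule). The Duration of treatment paragraph caps treatment at 48 weeks.
- **Delays.** "The treatment will be postponed if the patient experiences non-hematological AE grade" 2 or higher, with exceptions for fatigue and skin events; laboratory criteria also apply (Criteria for treatment modifications). A missed visit can move a vaccine too (Procedures regarding treatment). The limit is "If the treatment is postponed more than 6 weeks, patients will be excluded". Delays may recur: "A patient can be delayed several times during the course of treatment without being excluded" (Delayed treatment).
- **Progression.** "Treatment is terminated if disease progression occurs according to RECIST 1.1 at predefined evaluation time points" (Disease progression). These time points are not given as dates.
- **PFS.** It is an exploratory endpoint (Objectives and endpoints; Exploratory endpoints and objectives). No start date, event date or censoring rule is given.

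**The concern.** Progression seen on imaging is dated by the scan that finds it. If a late vaccine also makes the scan late, two patients whose tumours grow at the same time can be given different PFS times because one of them had a delay. Toxicity is one of the main reasons for delay, so the error is not spread evenly: patients with more delaying adverse events are, on average, credited with later progression. In an immunotherapy trial that could be misread as benefit going with immune toxicity. It would also distort a comparison of these patients' PFS with outside series scanned by calendar. With 10 patients of mixed tumour types, comparable scan timing is one of the few protections that a descriptive PFS has.

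**Working it through.** **1. The planned schedule reproduces.** Vaccine k falls at week 3(k − 1), so vaccine 16 is at week 45. The last evaluation is at 45 + 3 = week 48, which matches the stated 48 weeks. On-time scans fall at 3k for k = 4, 8, 12 and 16: weeks 12, 24, 36 and 48.

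**2. Permitted delays.** Here 6 weeks is taken as added to the 3-week interval. Each week of delay before a scan moves that scan and all later ones by a week.

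| Delay pattern | Scan weeks |
|---|---|
| None | 12, 24, 36, 48 |
| One 2-week delay in the first block of four | 14, 26, 38, 50 |
| One 6-week delay in the first block | 18, 30, 42, 54 |
| One 6-week delay in every block | 18, 36, 54, 72 |

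The extreme case is a 6-week delay before each of vaccines 2, 3 and 4: first scan at 12 + 18 = week 30. If 6 weeks means the whole gap between vaccines, one maximal delay gives 12 + 3 = week 15, and three give 6 + 6 + 6 + 3 = week 21. The direction is the same.

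**3. Effect on recorded PFS.** Assumptions, since the documents give no PFS figures: exponential time to progression with true median m; every progression dated at the next scheduled scan; no deaths or unscheduled scans; scans every 13 weeks after the fourth. Let S(t) = 2^(−t/m). Mean recorded PFS is the sum, over successive scans, of the gap to the next scan times S at the scan before it, starting from S(0) = 1.

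For m = 8, the 13-week tail is a geometric series with ratio 2^(−13/8) = 0.324:

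- On time: 12 + 12 × (0.3536 + 0.1250 + 0.0442) + 13 × 0.0156/(1 − 0.324) = 12 + 6.27 + 0.30 = 18.6 weeks.
- One 6-week delay in the first block: 18 + 12 × (0.2102 + 0.0743 + 0.0263) + 13 × 0.0093/(1 − 0.324) = 18 + 3.73 + 0.18 = 21.9 weeks.

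| Assumed true median (weeks) | On time | One 6-week delay, first block | 6-week delay in every block |
|---|---|---|---|
| 6 | 16.0 | 20.0 | 20.6 |
| 8 | 18.6 | 21.9 | 22.8 |
| 12 | 24.0 | 26.5 | 27.8 |
| 26 | 44.0 | 45.3 | 46.8 |

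A single 2-week delay adds about 0.3 to 1.2 weeks over the same range. True progression times are identical within each row.

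**4. Individual patients can go either way.** Progression at week 8 is dated week 12 on time and week 18 after the delay. Progression at week 14 is dated week 24 on time but week 18 after the delay. With one 6-week delay in the first block, about 17% (median 6 weeks) to 38% (median 26 weeks) of delayed patients record a shorter PFS; at a median of 8 weeks it is about 22%.

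**5. The 48-week maximum.** If it is a calendar cap and every interval is 9 weeks, vaccines fall at weeks 0, 9, 18, 27, 36 and 45. Six fit, and only the week-30 scan occurs. The documents do not say whether the cap or the count of 16 governs, or when such a patient is next scanned.

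**The case against.** The case against giving this much weight is substantial.

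- **Status of PFS.** It is exploratory, in 10 patients on one dose with no comparator and no PFS hypothesis. No analysis of PFS by toxicity is planned. This stands and limits the reach of the point.
- **The median.** A reader might infer that one or two delayed patients will shift the median. They can, but usually do not. In simulated trials of 10 under the assumptions above, one patient with a 6-week delay left the sample median unchanged in 65–86% of trials, and two left it unchanged in 47–71%. The average shift was 0.1–0.5 and 0.2–1.3 weeks respectively.
- **Size of delays.** The documents give no delay frequency and expect mild toxicity. Most other adverse events of grade 3 or higher exclude the patient, so toxicity delays would come mainly from grade 2 events and grade 3 laboratory values. A first scan at week 24 or 30 needs two or three maximal delays among the first four vaccines, on one reading of the limit.
- **Exposure without a scan.** A reader might infer that delayed patients get more vaccine before being scanned. They do not: it is four vaccines either way, and only calendar time is longer. Patients are also examined at every vaccine visit, and clinical judgement can end treatment at any time.
- **The sentence on consequences.** "Shorter delays can occur multiple times with no consequences for the patient or the trial" might be read as a claim about PFS. It follows a rule on stopping and exclusion under Unacceptable toxicity and concerns exclusion, so it should not be held against the plan here.
- **Reason for the design.** Imaging after a fixed number of vaccines is defensible when immune induction is slow, and it aligns the scan with the biopsy and DTH test after vaccine 4. That supports keeping the biopsy and DTH on the vaccine count. It does not make PFS comparable between patients.

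**Conclusion.** The point holds as a moderate weakness in an exploratory endpoint. Scan dates depend on vaccine delays, and nothing in the plan corrects for it. One 6-week delay in the first block moves the first scan from week 12 to week 18 (6/12 = 50% later). Mean recorded PFS then rises by 1.3 to 4.0 weeks across assumed true medians of 26 down to 6 weeks, and by 3.3 weeks at a median of 8. These figures rest on exponential progression, detection only at scheduled scans, and 6 weeks being added to the 3-week interval.

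The documents do not support the stronger reading that every patient with toxicity delays records a longer PFS. Some record a shorter one, deaths and progression found at unscheduled scans keep their own dates, and delays for any reason act the same way. What is affected is the descriptive PFS and any comparison by toxicity or with outside data. The primary safety endpoint and the secondary immune endpoint are not affected.

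**What to change.** - **Imaging.** Schedule scans from the date of the first vaccine at weeks 12, 24, 36 and 48, then every 12 weeks while the patient remains on treatment without progression. State a window, such as ±1 week, and say that the dates hold whatever the vaccine delays. The first four dates are the plan's own on-time dates.
- **Other assessments.** Keep the biopsy, DTH test and project blood samples tied to the vaccine count, and amend the header of the evaluation table so that it no longer covers imaging.
- **PFS definition.** Count from the first vaccine to the date of the scan showing progression, or to death, and add a censoring rule.
- **Passages to reconcile.** The 48-week maximum and the 16 vaccines cannot both hold once delays occur; the protocol must say which governs. Two further conflicts bear on delay and progression dates: the 6-week delay limit against the 12-week wording for unresolved grade 3–4 events, and the immune-related response criteria under Duration of treatment against RECIST 1.1 under Disease progression.

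The cost is mainly wording. A delayed patient may need separate visits for the scan and for the biopsy and DTH test, and occasionally one more scan if treatment runs past week 48.
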